2.1.4.3 Clinical Efficacy

[figure not shown]
Recently two phase 3 studies have been completed and the clinical study reports are under preparation. The primary efficacy endpoint for the studies was complete clearance of all treatable MC lesions at Week 12 in the ITT population. The proportion of subjects with complete clearance at each visit is shown in [Figure 2](#) and [Figure 3](#).

Figure 2 NI-MC301: Percentage of Subjects with Complete Clearance

Note: Subjects with missing lesion count data at the Week of interest were counted as non-responders.

Figure 3 NI-MC302: Percentage of Subjects with Complete Clearance

Note: Subjects with missing lesion count data at the Week of interest were counted as non-responders.

The proportion of subjects with complete clearance of all treatable molluscum lesions at Week 12 in NI-MC301 was 25.8% for SB206 and 21.6% for vehicle (p=0.375) and 30.0% for SB206 and 20.3% for vehicle (p=0.062) in NI-MC302. For the secondary endpoint, the proportion of subjects with complete clearance of all treatable molluscum lesions at Week 8 in NI-MC301 was 15.3% for SB206 and 10.3% for vehicle (p=0.202) and 13.9% for SB206 and 5.9% for vehicle (p=0.028) in NI-MC302. The results of other endpoints are available in the IB. The Kaplan-Meier analysis in both studies also support the effectiveness of SB206 by showing the reduction of time to complete clearance.

Analysis of the integrated data from NI-MC301 and NI-MC302 resulted in statistically significance for complete clearance at Week 12 (p= 0.038). Analysis of data from NI-MC302 study demonstrated substantial effectiveness for reducing lesions to 1 or 0 (p=0.011) and reducing lesions by at least 90% (p=0.002). SB206 demonstrated statistical effectiveness in complete clearance for up to 28%, reduced lesions to 1 or 0 for up to 39% and approximately 37% of subjects achieved a 90% reduction in lesions in NI-MC302. In addition, subjects treated with SB206 showed a lower occurrence of scarring when compared to the vehicle arm. Molluscum, caused by a family of pox viruses, is known to occasionally heal with small pitting (scar formation).”

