3 OBJECTIVES AND ENDPOINTS

Tier	Objectives	Endpoint(s)
Primary Efficacy	To evaluate the efficacy of SB206 10.3% as compared to Vehicle in subjects with molluscum contagiosum	The proportion of subjects with complete clearance of all treatable MC at Week 12
Secondary Efficacy Endpoints	To evaluate the efficacy of SB206 10.3% as compared to Vehicle in subjects with molluscum contagiosum	
 Proportion of subjects achieving a lesion count of 0 or 1 of all treatable MC at Week 12 Proportion of subjects achieving at least a 90% reduction from Baseline in the number of all treatable MC at Week 12 Proportion of subjects with complete clearance of all treatable MC at Week 8 Percent change from Baseline in the number of all treatable MC at Week 4
Safety endpoints	To evaluate the safety of SB206 10.3% compared to Vehicle in subjects with molluscum contagiosum	
 Incidence of treatment-emergent adverse events Change from Baseline in LSR scores Change from Baseline in abbreviated physical examinations Concomitant medications reported Proportion of subject(s) with reported scar(s)
Other Endpoint	To evaluate BOTE and SB206 10.3% compared to Vehicle in subjects with molluscum contagiosum	
 Change from Baseline in BOTE scores

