7.2.4 Scarring/Keloid Assessment

Scar formation (scars/keloids/hypertrophic scars) will be assessed starting at the Week 4 visit through Week 12 and again at Week 24. Using the lesion map as a guide, the investigator will assess the treated areas for scar/keloid formation. All scars, including keloid/hypertrophic scars, that develop after the Baseline assessment should be captured as AEs and assessed for relatedness to study treatment.

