10.3.4.1 Adverse Events

All AEs will be coded using the Medical Dictionary for Regulatory Activities (MedDRA Version 23.0 or later).

A treatment-emergent AE (TEAE) is defined as those AEs that occurred any time on or after the first in-clinical application of study drug through the last application of study drug and those existing AEs that worsened during this same period. If it cannot be determined whether the AE is treatment emergent due to a partial onset date, then it will be counted as such.

TEAEs will be summarized by System Organ Class (SOC) and Preferred Term (PT). For the summary by SOC and PT, each subject will be counted only once within a SOC or a PT. AEs with an outcome of death, SAEs, TEAEs leading to discontinuation from study treatment, and TEAEs leading to discontinuation from the study will be summarized similarly.

TEAEs will be further summarized by worst severity and highest relationship with study treatment, separately. For the summary by worst severity, each subject will be counted only once

within a SOC or PT according to the worst reported severity. Similarly, for the summary by highest relationship with study treatment, each subject will be counted only once within a SOC or PT according to the highest reported relationship with study treatment.

Separate listings will be provided for the AEs with an outcome of death, SAEs, TEAEs leading to discontinuation from study treatment, and TEAEs leading to discontinuation from study.

The proportion of subjects with scarring and the proportion of subjects with keloid or hypertrophic scarring will be summarized descriptively.

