## 6. GENERAL ANALYSIS CONSIDERATIONS

The statistical analyses will be reported using summary tables, listings, and figures (TLFs). The International Council for Harmonisation (ICH) numbering convention will be used for all TLFs. Unless otherwise noted, all statistical testing will be two-sided and will be performed at the 0.05 significance level. Tests will be declared statistically significant if the calculated  $P$ -value is  $\leq 0.05$ .

Continuous variable summaries will include the number of subjects ( $n$ ) with non-missing values, mean, standard deviation (SD), median, minimum, and maximum. Other statistics such as quartiles, confidence intervals (CIs), and number of missing values may be added as appropriate.

Categorical variable summaries will include the frequency and percentage of subjects who are in the category or each possible value. In general, the denominator for the percentage calculation will be based upon the total number of subjects in the study population within each treatment group, unless otherwise specified. The denominator for by-visit displays will be the number of subjects in the relevant study population with non-missing data at each visit.

All summary tables will be presented by treatment group. Baseline summaries will also include an overall summary column.

Individual subject data obtained from the eCRFs and any derived data will generally be presented by subject in data listings. Additionally, a listing of the subjects requiring a narrative because they experience one of the following events: serious adverse event, death, discontinued the study due to an AE, hypertrophic or keloid scarring, unresolved scars, or LSR suggestive of allergic contact dermatitis will be presented.

A separate report for the results from the study exit interview will be created.

The analyses described in this plan are considered a priori, in that they have been defined prior to breaking the blind.

Any analyses performed subsequent to breaking the blind will be considered post hoc and exploratory. Post hoc analyses will be labeled as such on the output and identified in the clinical study report.

All analyses and tabulations will be performed using SAS® software Version 9.4 or higher. Tables, listings, and figures will be presented in RTF format.

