#### 13.1 Adverse Events

Adverse event summaries restricted to treatment-emergent AEs (TEAEs) will include those AEs that occurred any time on or after the first in-clinical application of study drug through the last application of study drug and those existing AEs that worsened during this same period. If it cannot be determined whether the AE is treatment emergent due to a partial onset date, then it will be counted as such; see Appendix A for the imputation of missing dates algorithm. Post treatment AEs will include those AEs that occurred after the last application of study drug. Verbatim terms in the eCRFs will be mapped to preferred terms and system organ classes using the MedDRA Version 23.0 or later.

Each AE summary will be displayed by treatment group. Summaries that are displayed by system organ classes and preferred terms will be ordered by descending order of incidence in SB206 treatment group of system organ class and preferred term within each system organ class. Summaries of the following types will be presented:

- Overall summary of TEAEs and post treatment AEs that contain an overview of each item below.

- Subject incidence of TEAEs with total number of unique TEAEs and post treatment AEs with total number of unique post treatment AEs by MedDRA system organ class and preferred term.
- Subject incidence of TEAEs and post treatment AEs by MedDRA system organ class, preferred term, and maximum severity. At each level of subject summarization, a subject is classified according to the maximum severity if the subject reported 1 or more events. Adverse events with missing severity will be considered severe for this summary.
- Subject incidence of TEAEs by MedDRA system organ class, preferred term, and closest relationship to study drug (Related/Not Related). Related AEs are those reported as “Definite,” “Probable,” or “Possible,” and unrelated AEs are those reported as “Unlikely” or “Unrelated.” At each level of subject summarization, a subject is classified according to the closest relationship if the subject reported 1 or more events. Adverse events with a missing relationship will be considered related for this summary.
- Subject incidence of serious TEAEs with total number of unique serious TEAEs and post treatment serious AEs with total number of unique post treatment serious AEs by MedDRA system organ class and preferred term.

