- Subject incidence of TEAEs leading to study drug discontinuation by MedDRA system organ class and preferred term.
- Subject incidence of TEAEs leading to study discontinuation and post treatment AEs leading to study discontinuation by MedDRA system organ class and preferred term.
- Subject incidence of TEAEs leading to death as an outcome by MedDRA system organ class and preferred term.
- Subject incidence of Transient TEAEs, identified based on a search of verbatim terms containing ‘TRANSIENT’.

Separate listings of all AEs, all SAEs, all TEAEs leading to study drug discontinuation, all AEs leading to study discontinuation, ongoing treatment related AEs, and all post treatment AEs will be provided.

The proportion of subjects with scarring and the proportion of subjects with keloid or hypertrophic scarring will be summarized descriptively at each visit.

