14.3.1.6	Summary of Treatment-Emergent Adverse Events Leading to Study Drug Discontinuation by System Organ Class and Preferred Term	Safety

Table Number	Table Title	Analysis Population
14.3.1.7	Summary of Treatment-Emergent Adverse Events Leading to Death by System Organ Class and Preferred Term	Safety
14.3.1.8.1	Summary of Treatment-Emergent Adverse Events Leading to Study Discontinuation by System Organ Class and Preferred Term	Safety
14.3.1.8.2	Summary of Post Treatment Adverse Events Leading to Study Discontinuation by System Organ Class and Preferred Term	Safety
14.3.1.9	Summary of Transient Treatment-Emergent Adverse Events by System Organ Class and Preferred Term	Safety
14.3.2	Listings of deaths, other serious and significant adverse events	
14.3.2.1	Listing of Serious Adverse Events	Safety
14.3.2.2	Listing of Adverse Events Leading to Study Drug Discontinuation	Safety
14.3.2.3	Listing of Deaths	Safety
14.3.6	Other safety data	
14.3.6.1.1	Summary of Local Skin Reaction (LSR) Composite Score by Visit	Safety
14.3.6.1.2	Summary of Local Skin Reaction (LSR) Score Results by Visit	Safety
14.3.6.1.3	Shift Summary of Local Skin Reaction (LSR) Score Results by Visit	Safety
14.3.6.1.4	Summary of Local Skin Reaction (LSR) Composite Score by Dichotomized Baseline BOTE Score and Visit	Safety
14.3.6.1.5	Summary of Local Skin Reaction (LSR) Individual Score by Dichotomized Baseline BOTE Score and Visit	Safety
14.3.6.2	Summary of Events of Special Interest	Safety
14.3.6.3	Summary of Physical Examination Findings	Safety
14.3.6.4	Summary of Scarring and Keloid by Visit	Safety
14.3.6.5	Summary of Patch Testing Results	Safety

Figure Number	Figure Title	Analysis Population
14.2.1.5	Forest Plot: Odds Ratio (95% CI) of the Proportion of Subjects with Complete Clearance at Week 12	ITT
14.2.2.4.2	Percent Change from Baseline in Lesion Count over Time by Treatment Group	ITT
14.2.3.4.2	Mean Change from Baseline in Lesion Count over Time by Treatment Group	ITT
14.2.3.6.2	Kaplan-Meier Plot of Time to Complete Clearance (Days) from Start of Dosing	ITT
14.2.3.9.2	Cumulative Distribution Function Plot Across Subject Global Severity Assessment Responses	ITT
14.2.3.9.3	Cumulative Distribution Function Plot by Subject Global Severity Assessment Severity Category	ITT
14.2.3.10.2	Cumulative Distribution Function Plot Across Subject Global Impression of Change Responses	ITT

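### No listed table gives the proportion of subjects ever scarred: the SAP reports scarring only visit by visit and splits scar AEs at the last application, although the protocol's scar endpoint has no visit restriction

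*SAP*

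**What the plan says.** Protocol section 3 lists as a safety endpoint "Proportion of subject(s) with reported scar(s", with no visit attached. Protocol 10.3.4.1 plans its analysis, again without a visit: "The proportion of subjects with scarring and the proportion of subjects with keloid or hypertrophic scarring will be summarized descriptively". Under Protocol 7.2.4, scarring "will be assessed starting at the Week 4 visit through Week 12 and again at Week 24", which gives four scheduled checks (Weeks 4, 8, 12 and 24), and every scar that appears after Baseline is also recorded as an AE.

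SAP 13.1 repeats the protocol sentence and adds a visit restriction: "The proportion of subjects with scarring and the proportion of subjects with keloid or hypertrophic scarring will be summarized descriptively at each visit". The one scar table in SAP Appendix C is Table 14.3.6.4, "Summary of Scarring and Keloid by Visit". SAP section 6 sets its denominator: "The denominator for by-visit displays will be the number of subjects in the relevant study population with non-missing data at each visit". SAP section 14 declares no change from the protocol's methods.

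For AEs, SAP 13.1 ends the treatment-emergent (TEAE) window at the last application and handles the rest separately: "Post treatment AEs will include those AEs that occurred after the last application of study drug".

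**The concern.** A proportion of subjects with a scar is one number per arm. Four proportions on four changing denominators are not that number, and the SAP does not say that the visit figures are cumulative. A subject with a scar noted at Week 8 who then leaves is in the Week 8 column but in neither the numerator nor the denominator afterwards.

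The AE tables might be expected to fill the gap, but they cut each subject's follow-up at the last application. That date depends on response: the investigator may stop drug on clearance (Protocol 4.1), and the Week 12 dose is given only to subjects who still have lesions (Protocol 6.7.7).

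Scarring also bears on the sponsor's case for the product. Protocol 2.1.4.3 reports of the earlier studies that "subjects treated with SB206 showed a lower occurrence of scarring when compared to the vehicle arm", and Protocol 2.2 gives avoidance of scarring as part of the rationale. An outcome used in this way needs one per-arm figure fixed in advance.

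**Working it through.** The plan states no figure for this endpoint, so the first step is to trace every listed output that could carry it.

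| Output (SAP 13.1, 13.3, Appendix C) | Scars counted | Proportion ever scarred? |
|---|---|---|
| Table 14.3.6.4 | Scars at each visit, over subjects with data at that visit | No |
| Table 14.3.1.2.1 (TEAEs) | Onset from first through last application | No |
| Table 14.3.1.2.2 (post-treatment AEs) | Onset after last application | No |
| Table 14.3.6.2 (special interest) | Application-site TEAEs only | No |
| Listings 16.2.7.1 and 16.2.9.4 | All AEs; all scar assessments | Subject data, no proportion |

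The overall AE summary is also listed as two tables (14.3.1.1.1 and 14.3.1.1.2), one for each window.

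**What the two AE tables identify.** Let T be the subjects with a treatment-emergent scar, P those with a post-treatment scar, and B those with scar events in both windows. The number ever scarred is E = T + P − B. B is not reported, so max(T, P) ≤ E ≤ T + P. With assumed counts in an arm of 425:

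- T = 15, P = 15: E is 15 to 30, that is 15/425 = 3.5% to 30/425 = 7.1%.
- T = 20, P = 10: E is 20 to 30, that is 20/425 = 4.7% to 30/425 = 7.1%.

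**What the visit table identifies.** For scars found at the scheduled checks, E lies between the largest visit count and the sum of the four. With an assumed 15 at each visit and all 425 attending, that is 15 to 60 subjects, or 3.5% to 60/425 = 14.1%. Denominators also shrink. Suppose dropout matched the 15.3% and 17.2% of the earlier studies (Protocol 2.1) and none of those subjects had a Week 24 record. The Week 24 denominator would then be 425 × 0.847 = 360 or 425 × 0.828 = 352, and the same 15 subjects would read as 4.2% or 4.3%.

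**Scale.** Application site scar in Protocol Tables 3 and 4 reproduces as printed. On SB206 it is 6/235 = 2.6% and 10/237 = 4.2%; on vehicle, 9/116 = 7.8% and 10/117 = 8.5%. Pooled, this is 16/472 = 3.4% against 19/233 = 8.2%, a difference of 4.8 points. The first illustration above is 7.1 − 3.5 = 3.5 points wide before rounding (15/425), which is smaller than that difference but of the same order.

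**Does the split favour an arm?** Week 8 clearance from Protocol 2.1.4.3, weighted by the safety counts, is:

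- SB206: (15.3% × 235 + 13.9% × 237)/472 = 14.6%, about 62 of 425.
- Vehicle: (10.3% × 116 + 5.9% × 117)/233 = 8.1%, about 34 of 425.

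These are subjects who could have stopped drug early. They are not misclassified scars. If their scar risk equals the pooled arm rate, they would contribute 62 × 3.4% = 2.1 scarred subjects on SB206 and 34 × 8.2% = 2.8 on vehicle, or 0.5% and 0.7% of an arm. Even if all of these scars moved out of the TEAE table, vehicle would lose slightly more in absolute terms. SB206 would lose the larger share of its scars (14.6% against 8.1%). The direction depends on the measure, and the size is two or three subjects per arm.

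**The case against.** The case on the other side has four parts.

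- **The endpoint has no time frame.** Reading it as over the whole study is an interpretation, and by-visit reporting suits an outcome assessed at visits. This stands in part. By-visit rows are legitimate, but they do not deliver a single proportion of subjects, and the protocol's summary was not limited to visits.
- **Post-treatment scars are not lost.** They have their own table, and the two counts sum to the total except for subjects with separate scar events in both windows. This stands as a limit on size. The low end of each range above needs the greatest possible overlap, which is unlikely, and the counts are assumed. The overlap is nevertheless not reported.
- **The shells are in a separate file, and Appendix C allows minor changes to the index.** An any-visit row in Table 14.3.6.4 cannot be excluded. But neither the SAP text nor the table title provides one, and the stated rule is what binds the analysis.
- **The listings hold the data, and no inference is planned for safety.** Both are true, so the consequence is modest. But the Week 12 data are unblinded before follow-up ends, and SAP section 6 classes any analysis added after unblinding as post hoc. A figure derived later from listings would carry that label.

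**Conclusion.** The point holds as a gap in planned reporting. The protocol sets a per-subject scar endpoint without a visit restriction. The SAP narrows it to visits without declaring a change, and no listed table gives the proportion ever scarred. The listed tables only bound it; on the assumed counts the AE tables leave a range of up to 3.5 points in an arm of 425. This rests on the SAP text and table titles, since the shells cannot be seen.

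A reader might go further and infer that every scar seen at Week 24, and every scar in a subject who stopped for clearance, drops out of the TEAE table. The documents do not support that. SAP 13.1 classes an AE by when it occurred, so a scar that began on treatment stays a TEAE however late it is seen. Drug may be restarted if lesions recur, which moves the last application later. Onsets that partial dates cannot place are counted as treatment-emergent.

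A reader might also infer that the TEAE scar rate is understated more on SB206. The TEAE window may differ between arms because stopping depends on clearance, but neither the direction nor the size of a bias is established.

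Only a descriptive safety endpoint is affected. The primary and secondary efficacy analyses and their error control are untouched.

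**What to change.** In SAP 13.1, define the endpoint as the number and percentage of Safety Population subjects in each arm with at least one scar, and separately with at least one keloid or hypertrophic scar, reported at any time after Baseline through Week 24, whatever the date of last application. Use the full Safety Population as a fixed denominator. Add these rows to Table 14.3.6.4 and keep the by-visit rows as supportive. The change should be made before the Week 12 unblinding. It costs one sentence and added table rows on data already collected.

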### **13.2 Local Skin Reaction**

The LSR composite score will be calculated by summing up all the numerical responses (0-4) to each individual parameter for a composite score that ranges between 0 and 24. The observed and change from Baseline values of the LSR composite score will be summarized descriptively at each visit. This analysis will be repeated based on the dichotomized baseline BOTE score described in Section 12.

A table summarizing each LSR parameter (erythema, flaking/scaling, crusting, swelling, vesiculation/pustulation, and erosion/ulceration) score at each scheduled post-baseline assessment will be presented. This analysis will be repeated based on the dichotomized baseline BOTE score described in Section 12.

Additionally, a shift table comparing the baseline score for each LSR parameter to each scheduled postbaseline assessment will be presented for the Safety Population.

### **13.3 Events of Special Interest**

Events of Special Interest will include subjects with any TEAE where the preferred term contains “application site”, subjects with at least 1 post-baseline occurrence of moderate BOTE inflammation score, or subjects with at least 1 post-baseline LSR component score  $\geq 1$ . A summary including the number and percentage of subjects with at least 1 event of special interest, AEs of interest by MedDRA system organ class and preferred term, at least 1 moderate BOTE inflammation score, and any LSR component score  $\geq 1$  will be provided for the Safety Population. The analysis will also be repeated with the LSR criteria revised to include any post-baseline LSR component (excluding erythema) score  $\geq 1$  and erythema score  $\geq 2$ .

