2.1.4.2 Clinical Safety

It should be noted some subjects have experienced transient asymptomatic erythema at the application site within 5 minutes of dosing, which typically lasted ≤ 15 minutes. This is due to nitric oxide's vasodilatory pharmacologic effect and is an expected event.

Summaries of the safety analyses of the phase 3 studies ([NI-MC301](#) and [302](#)) are ongoing, and the CSRs are under preparation. The treatment emergent adverse event (TEAE) profile of SB206 through the Week 24 was found to be favorable and was very similar between the two studies. Study drug discontinuations in the SB206 treatment arm were all due to application site reactions and no treatment-related serious adverse events were reported across both studies.

Table 2 Overall Summary of TEAEs (Safety Population) through Week 24

	NI-MC301		NI-MC302	
	Vehicle (n=116)	SB206 (n=235)	Vehicle (n=117)	SB206 (n=237)
Subjects who reported at least one TEAE	36 (31.0%)	115 (48.9%)	30 (25.6%)	120 (50.6%)
Serious TEAE	0	0	1 (0.9%)	1 (0.4%)
Treatment-related TEAE	19 (16.4%)	86 (36.6%)	8 (6.8%)	86 (36.3%)
TEAE leading to study drug discontinuation	1 (0.9%)	7 (3.0%)	1 (0.9%)	17 (7.2%)

The TEAEs reported in greater than 5% of subjects in the SB206 treated groups were application site pain and application site erythema, with the majority of these TEAEs being mild or moderate in severity.

Table 3 TEAEs in $\geq 2\%$ of subjects in either SB206 treated group or Vehicle group (NI-MC301)

	Vehicle (n=116)			SB206 (n=235)		
	Mild	Moderate	Severe	Mild	Moderate	Severe
Application site pain	8 (6.9%)	0	0	34 (14.5%)	16 (6.8%)	1 (0.4%)
Application site erythema	2 (1.7%)	1 (0.9%)	0	13 (5.5%)	15 (6.4%)	1 (0.4%)
Application site pruritus	0	0	0	8 (3.4%)	2 (0.9%)	1 (0.4%)
Pyrexia	3 (2.6%)	1 (0.9%)	0	7 (3.0%)	4 (1.7%)	0
Application site exfoliation	0	0	0	4 (1.7%)	5 (2.1%)	1 (0.4%)
Application site scar	9 (7.8%)	0	0	6 (2.6%)	0	0
Application site swelling	1 (0.9%)	0	0	5 (2.1%)	1 (0.4%)	0
Application site dermatitis	1 (0.9%)	0	0	1 (0.4%)	3 (1.3%)	1 (0.4%)
Application site discolouration	0	0	0	5 (2.1%)	0	0
Vomiting	1 (0.9%)	0	0	2 (0.9%)	5 (2.1%)	0
Upper respiratory tract infection	2 (1.7%)	0	0	3 (1.3%)	2 (0.9%)	0

Table 4 TEAEs in $\geq 2\%$ of subjects in either SB206 treated group or Vehicle group (NI-MC302)

[figure not shown]
	Vehicle (n=117)			SB206 (n=237)		
	mild	moderate	severe	mild	moderate	severe
Application site pain	1 (0.9%)	1 (0.9%)	0	15 (6.3%)	22 (9.3%)	0

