Application site erythema	0	0	0	10 (4.2%)	14 (5.9%)	2 (0.8%)
Application site dermatitis	1 (0.9%)	0	0	6 (2.5%)	5 (2.1%)	0
Application site scar	10 (8.5%)	0	0	10 (4.2%)	0	0
Application site exfoliation	0	0	0	3 (1.3%)	5 (2.1%)	1 (0.4%)
Application site pruritus	1 (0.9%)	1 (0.9%)	0	3 (1.3%)	5 (2.1%)	0
Application site swelling	0	0	0	1 (0.4%)	5 (2.1%)	1 (0.4%)
Pyrexia	2 (1.7%)	0	0	5 (2.1%)	2 (0.8%)	0
Application site vesicles	0	0	0	0	5 (2.1%)	0
Dermatitis contact	0	0	0	3 (1.3%)	3 (1.3%)	0

Additional details regarding safety are available in the [Investigators Brochure \(IB\)](#).

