7.2.5 Diagnosis of Allergic Contact Dermatitis and Patch Testing

After treatment is reintroduced post-LSR, if a subject experiences a stronger LSR (second LSR event) than the first LSR event, allergic contact dermatitis may be suspected. In order to confirm whether the reaction is allergic contact dermatitis, patch testing should be conducted. If the investigator determines that patch testing is appropriate, he/she should contact the CRO medical monitor to discuss next steps. Patch testing supplies will be provided once requested from the CRO medical monitor. Additional drug product for patch testing may be supplied through IWRS if the currently assigned subject's investigational product was assigned more than 60 days prior to the patch testing date(s) or if the subject had previously returned all their drug product.

Additionally, patch testing should be discussed with the subject/caregiver. If the subject/caregiver consents to patch testing and once the LSR has been completely resolved for a period of 2 weeks and up to 2 months, patch testing will commence. If allergic contact dermatitis is suspected, study drug should be permanently discontinued and an AE of allergic contact dermatitis should be recorded as the reason for discontinuation. Week 12/ET assessments should be completed at the time of discontinuation.

In the event of suspected allergic contact dermatitis developed, photographs may be taken of the affected area(s) and transmitted to the CRO medical monitor for review prior to initiating patch testing. See [Appendix 1](#) for further information.

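### SAP 13.3 finds adverse events of special interest only by the string 'application site', so its AE rows cannot show 'Dermatitis contact' and may omit suspected allergic contact dermatitis

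*SAP*

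**What the plan says.** SAP 13.3 gives three alternative ways for a subject to have an event of special interest:

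- an adverse event: "subjects with any TEAE where the preferred term contains" the string 'application site';
- a BOTE score: "subjects with at least 1 post-baseline occurrence of moderate BOTE inflammation score";
- a local skin reaction (LSR): "subjects with at least 1 post-baseline LSR component score" of 1 or more.

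The output gives the number of subjects with any such event and, separately, "AEs of interest by MedDRA system organ class and preferred term". A planned repeat of the analysis changes the LSR cut-offs and leaves the AE search as it is.

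Two places in the protocol bear on the search string. Table 4 (section 2.1.4.2, NI-MC302) has a row for "Dermatitis contact" that is separate from its row for 'Application site dermatitis'. Section 7.2.5 says that when allergic contact dermatitis is suspected, "an AE of allergic contact dermatitis should be recorded as the reason for discontinuation". Appendix 1 then sets out the patch-test procedure.

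**The concern.** A special-interest table should gather the reactions already known to matter for this product. The protocol singles out suspected allergic contact dermatitis: it has its own recording rule, its own appendix, and patch-test results that go to the DSMB. The AE part of SAP 13.3 nevertheless contains no term for it. It relies on the dictionary term happening to include two particular words, and the sponsor's own earlier table shows a contact dermatitis term that does not include them.

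If the SAP is followed as written, a reader who looks in the special-interest table for sensitization-type events, by arm and by preferred term, could find none and conclude that none occurred.

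**Working it through.** **1. Which earlier terms does the string match?**

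| Preferred term (protocol Tables 3 and 4) | Contains 'application site'? | NI-MC301, vehicle vs SB206 | NI-MC302, vehicle vs SB206 |
|---|---|---|---|
| Dermatitis contact | No | not listed | 0/117 vs 6/237 |
| Application site dermatitis | Yes | 1/116 vs 5/235 | 1/117 vs 11/237 |
| Application site scar | Yes | 9/116 vs 6/235 | 10/117 vs 10/237 |

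Counts are summed over the severity columns, taking each subject to appear once per term.

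**2. The NI-MC302 figure.** The Table 4 row reads "Dermatitis contact 0 0 0 3 (1.3%) 3 (1.3%) 0". Each SB206 cell reproduces: 3/237 = 1.3%. The total is 3 + 3 = 6, and 6/237 = 2.5% (exact 95% interval 0.9% to 5.4%), against 0/117 on vehicle. The two-sided Fisher test gives p = 0.18.

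**3. What NI-MC301 adds.** Table 3 lists terms reached by at least 2% of either arm. On SB206, 5/235 = 2.1% would be listed and 4/235 = 1.7% would not. Table 3 does list terms with exactly 5 SB206 subjects, such as application site dermatitis (1 + 3 + 1). 'Dermatitis contact' is absent, so NI-MC301 had between 0 and 4 SB206 cases. On vehicle, 2/116 = 1.7% falls below the cut-off and 3/116 = 2.6% does not, so there were between 0 and 2 vehicle cases.

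**4. Pooled range and projection to this trial (425 per arm, SAP section 5).**

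- SB206: 6/472 = 1.3% up to (6 + 4)/472 = 2.1%. Then 425 × 6/472 = 5.4 and 425 × 10/472 = 9.0, or about 5 to 9 subjects.
- Vehicle: 0/233 up to 2/233 = 0.9%, or 0 to about 4 subjects (425 × 2/233 = 3.6).
- NI-MC302 alone: 425 × 6/237 = 10.8. Its interval gives about 4 to 23 subjects.

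**5. Can the other two parts stand in for the AE part?** The LSR part may count such a subject, because a score of 1 on any component is enough, including erythema described only as slightly pink. It does not record what the event was. LSRs are also scored at scheduled visits (protocol 7.2.3), so a reaction that settles between visits may not be scored. The BOTE part does not identify the event either. Only the rows by preferred term can name it.

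**6. Scars.** "Application site scar" does match the string and was commoner on vehicle: 9/116 = 7.8% vs 6/235 = 2.6% in NI-MC301 (p = 0.045), and 10/117 = 8.5% vs 10/237 = 4.2% in NI-MC302 (p = 0.14). Across the application-site terms listed in the two tables (subject-by-term counts, not de-duplicated), scars are (9 + 10)/(22 + 15) = 19/37 = 51% on vehicle and (6 + 10)/(123 + 113) = 16/236 = 7% on SB206.

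**The case against.** The strongest reply is that nothing is lost from the report. Contact dermatitis with onset on treatment appears in the TEAE tables by preferred term, severity and relationship (SAP 13.1). Under protocol 7.2.5, suspected allergic contact dermatitis is recorded as the reason for stopping study drug, so it also belongs in the table of TEAEs leading to study drug discontinuation. SAP section 6 requires narratives for LSRs suggestive of it. A patch-test listing is planned, with a table indexed in Appendix C, although section 13.6 makes that table optional. No test is attached to any safety endpoint. All of this stands, and it limits the consequence to the special-interest table.

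Three stronger readings are tempting, and the documents do not support them.

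- *A reader might infer that the six NI-MC302 cases were sensitization reactions that SAP 13.3 would miss.* Neither document says they were allergic or patch-test positive, nor which preferred term a report of allergic contact dermatitis is coded to. The larger dermatitis term in that trial, 'Application site dermatitis', is captured.
- *A reader might project about 11 missing SB206 subjects.* That uses NI-MC302 alone and ignores NI-MC301, where the term stayed below 2%.
- *A reader might say that including scars makes the AE rows wrong or hides an SB206 excess.* Scars get their own preferred-term row and so change no other such row. They also have a separate by-visit summary (SAP 13.1). Section 13.3 defines no local-reaction total that they would distort. Only an aggregate application-site row would be diluted. Because the protocol records all scars as adverse events and lists scarring as a safety endpoint, including them is defensible.

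**Conclusion.** The point holds within a narrow scope. The search in SAP 13.3 cannot return 'Dermatitis contact', and it may not return events recorded as the protocol directs for suspected sensitization. At the earlier rates, about 5 to 9 of 425 SB206 subjects would be missing from the special-interest AE rows under that term. This assumes that the rate recurs, that coding practice is unchanged, and that the NI-MC301 count lies anywhere from 0 to 4. The 6 vs 0 split in NI-MC302 is compatible with chance and does not establish an arm difference. The case for change is that the definition should cover a reaction the protocol already treats as special. Whether allergic contact dermatitis itself would be missed depends on coding that the documents do not show. No efficacy result, hypothesis test or general AE table is affected.

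**What to change.** Before unblinding, redefine the AE part of SAP 13.3 as a TEAE that meets any of the following:

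- the preferred term contains 'application site';
- the preferred term is 'Dermatitis contact' or another contact or allergic dermatitis term on a list fixed in advance;
- the event was reported as allergic contact dermatitis or suspected allergic contact dermatitis, whatever term it was coded to.

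The third condition needs a search of reported terms. SAP 13.1 already plans one of that kind for transient events.

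Optionally, if any aggregate application-site AE row is shown, give it with and without 'Application site scar'.

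The cost is a few lines of SAP text and a term list. No new data are needed, and only one descriptive table changes.
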